1.1 Primary Objectives

- 1.1.1 To determine the effect of PROSTVAC® on the change (from pre to post-intervention) in CD8⁺ positive cells in the stroma adjacent to tumor and within the malignant portion of the prostate biopsies.
- 1.1.2 To determine the effect of PROSTVAC® on the change in CD4⁺ positive cells in the stroma adjacent to tumor and within the malignant portion of the prostate biopsies.

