3. SUMMARY OF STUDY PLAN

This is a Phase II randomized, placebo-controlled, double-blind trial of PROSTVAC® in patients with clinically localized prostate cancer undergoing active surveillance. We plan to recruit men with a diagnosis of localized prostate cancer who are being monitored by active surveillance. Detailed inclusion and exclusion criteria are listed in sections 4.1 and 4.2.

Participants will undergo a screening evaluation in which the informed consent form and medical records and tissue release form will be signed in order to obtain information from urologic assessment, biopsy pathology reports, PSA test results, and biopsy tissues. Participants will undergo a brief physical exam and be evaluated for concomitant medications, medical history and baseline symptoms and signs. International Prostate Symptom Score (IPSS) will be obtained. Blood will be collected for complete blood count with differentiation (CBC-diff), comprehensive metabolic panel (CMP), and PSA. Screening visit procedures, including PSA, performed within 90 days prior to the Baseline Visit (first vaccine injection), may be applied toward eligibility.

Participants will also undergo a digital rectal exam (DRE) to confirm clinical stage at screening, if a DRE has not been performed within 180 days before the Baseline Visit.

Following the screening evaluation, eligible participants will be randomized 2:1 to receive PROSTVAC® or placebo. Randomization will be stratified according to the study site and the number of repeat biopsies following diagnosis (≤ 2, or >2). We plan to randomize 150 eligible men (i.e., 100 receiving PROSTVAC® and 50 receiving placebo).

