4. PARTICIPANT SELECTION

4.1 Inclusion Criteria

- 4.1.1 Biopsy-proven (consisting of ≥ 10 tissue cores) adenocarcinoma of the prostate with cancer present in at least one biopsy core, either random or targeted, in the most recent biopsy.
- 4.1.2 All prior biopsies must meet the following: $\leq 50\%$ of the total number of random biopsy cores positive for cancer
 - Gleason score $\leq (3+4)$
- 4.1.3 Clinical stage $\leq T2a$ by DRE
- 4.1.4 Biopsies performed at outside institutions should have Gleason score confirmed at the study site by a GU pathologist to ensure eligibility.
- 4.1.5 Pre-intervention biopsy tissue (most proximal to enrollment) containing sufficient tumor tissue to cut 5-10 unstained slides confirmed to be available upon request.
- 4.1.6 Screening serum PSA < 20 ng/mL. For men treated with 5-alpha-reductase inhibitors (e.g., finasteride, dutasteride), PSA needs to be < 10 ng/mL.
- 4.1.7 Hematological eligibility parameters:
Neutrophil count $\geq 1,200/\text{mm}^3$ (≥ 1.2 k/ μL)
Stable platelet count $\geq 75,000/\text{mm}^3$ (≥ 75 k/ μL)
- 4.1.8 Hepatic and renal function eligibility parameters:
Bilirubin ≤ 1.5 mg/dL (or ≤ 3.0 mg/dL for patients with Gilbert's syndrome)
ALT and AST ≤ 2.5 x ULN
Serum creatinine ≤ 1.5 x ULN
- 4.1.9 Karnofsky $\geq 70\%$; see Appendix A.
- 4.1.10 Must agree to use medically acceptable barrier and/or chemical method of contraception while on study and for at least one month following the last vaccine injection because the effects of PROSTVAC® on the developing human fetus at the recommended therapeutic dose are unknown. Should a participant's partner become pregnant or suspect she is pregnant while the participant is participating in this study, the study physician should be informed immediately. In the event a participant's partner becomes pregnant, the study sponsor may request additional information regarding the course of the pregnancy and if the pregnancy is carried to term, the birth of the child (i.e., the outcome of the pregnancy).
- 4.1.11 Ability to understand and the willingness to sign a written informed consent document.
- 4.1.12 No planned prostate biopsies during the intervention until after the post-intervention biopsy.
- 4.1.13 Men on stable doses of 5-alpha reductase inhibitors are eligible as long as there is no planned dose change while on study.

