⁹At the Day 84 visit, CBC-diff and CMP will need to be evaluated to determine whether the injection on that day may be given or omitted and whether there is the need to repeat the safety labs before the next scheduled injection. If needed, the labs can be done on a different day prior to the day for the vaccine injection, but the labs and the vaccine injection should fall within the window specified on the schedule of events.

¹⁰Subjects to be followed for 30 days after the last study dose is given. Participants will be asked to keep a 30-day diary and mail it back to the study staff in a pre-addressed, stamped envelope.

¹¹6 months (5-7 months) following the post-intervention biopsy or 6 months (5-7 months) after the last study dose is given, if no post-intervention biopsy was performed, to be performed as part of the standard-of-care.

¹²If available, reports from the prostate MRI scans (and companion pathology reports) performed from 3 years prior to and 6 months after the study intervention will be collected and submitted to the University of Arizona to capture the lesion size information.

¹³Patients who have undergone prostatectomy, radiation therapy or focal prostate cancer therapy are exempt from the six-month follow-up visit requirement.

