13.4 Primary Objective, Endpoint(s), Analysis Plan

The primary objectives of this study are to determine the effects of PROSTVAC® on the change (from pre- to post-intervention) in CD8⁺ and CD4⁺ positive cells in the stroma adjacent to tumor and within the malignant portion of the prostate biopsies.

The primary endpoints are the change in CD8⁺ and CD4⁺ positive cells in the stroma adjacent to tumor and within the malignant portion of the prostate biopsies. The change in CD8⁺ and CD4⁺ positive cells will be compared between participants treated with PROSTVAC® and those treated with placebo. We project an attrition rate of 10% (with respect to completing the intervention and providing post intervention biopsy) and 70% of the post intervention biopsy would have tumor. We plan to randomize 150 eligible participants to receive PROSTVAC® or placebo at a 2:1 ratio to have 63 and 31 subjects in the PROSTVAC® group and the placebo group, respectively, with primary endpoint data. A two-sided two-sample t test will be used to compare the change in CD4⁺ and CD8⁺ positive cells in tumor tissue between the treatment and placebo groups. Based on a sample size of 63 in the PROSTVAC® group and 31 in the placebo group and assuming that the standard deviation of the change in CD8⁺ and CD4⁺ positive cells for the PROSTVAC group is twice that of the placebo group, the power will be at least 90% to detect a Cohen's d effect size (i.e. the difference between the two groups divided by the pooled standard deviation) of ≥ 0.63 at a significance level of 5% by the Bonferroni correction (i.e., a significance level of 2.5% for each). MI techniques will be performed, as needed, for the participants without endpoint data. If MI is deemed necessary, the variables that are predictive of missing endpoint data will be incorporated into MI. The "available" sample size after MI is expected to be larger than the estimated sample size. Hence, we are confident of detecting effect sizes smaller than the above effect sizes after applying the Rubin's rules since the predictive variables used in MI can improve efficiency and reduce potential bias due to missing data.

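### The baseline biopsy for the co-primary CD8 and CD4 changes has no maximum age and the analysis ignores its age; this can add variance and cost power, and adjusting for the interval is nearly free.

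*Combined protocol and SAP*

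**What the plan says.** The co-primary endpoint for CD8 is the "change (from pre to post-intervention) in CD8⁺ positive cells in the stroma adjacent to tumor and within the malignant portion of the prostate biopsies"; CD4 is defined in parallel (1.1, 8.1). The tissue baseline is fixed by 4.1.5: "Pre-intervention biopsy tissue (most proximal to enrollment) containing sufficient tumor tissue to cut 5-10 unstained slides confirmed to be available upon request". It also serves PD-L1 (8.2.1) and tumor extent (8.2.6), and 4.1.2 holds grade on all prior biopsies to Gleason 3+4 or below. No section sets a maximum age for it.

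Other baseline items do have windows. Screening procedures, PSA included, "performed within 90 days prior to the Baseline Visit (first vaccine injection), may be applied toward eligibility" (Section 3), and a DRE may be up to 180 days old (Section 3, 7.2). The post-intervention biopsy follows 7 to 14 days after the last scheduled dose on Day 140 (7.4), so at about Day 147 to 154.

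Randomization is stratified by site and number of repeat biopsies, 2 or fewer versus more than 2 (13.2). For the primary analysis, "A two-sided two-sample t test will be used to compare the change" (13.4), and 13.4 and 13.5 name no covariates. The secondary analyses are declared exploratory (13.5).

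**The concern.** The pre-to-post change covers the treated period plus whatever time passed between the last biopsy and Day 0. The vaccine cannot affect that earlier time, and its length may differ widely between men. Stratifying on the number of repeat biopsies does not control the age of the latest one.

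Two different costs need to be kept apart. For continuous changes, time-related drift before Day 0 adds spread to the change scores and so lowers power, including for both co-primary endpoints. For the binary grade endpoint, upgrading that occurred before Day 0 but had not been sampled is counted as progression on study in either arm, which moves the risk ratio toward 1.

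A further consequence is that a change within one arm cannot be read as a treatment effect. Changes in PSA (drawn at the Baseline Visit) and IPSS (taken at screening) are not affected.

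**Working it through.** **1. The plan's own figures.** Inputs from 13.2 and 13.4: 100 and 50 randomized, 10% attrition, tumor in 70% of post-intervention biopsies. Evaluable: 100 × 0.9 × 0.7 = 63 and 50 × 0.9 × 0.7 = 31.5 (31 stated). This reproduces.

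Power inputs: "the power will be at least 90% to detect a Cohen's d effect size", here a d of 0.63 scaled on the pooled SD; testing "at a significance level of 5% by the Bonferroni correction (i.e., a significance level of 2.5% for each"; and an SD for PROSTVAC twice that for placebo. Setting the placebo SD to 1:
- Pooled SD = √[(62 × 4 + 30 × 1)/92] = 1.738, so the difference is 0.63 × 1.738 = 1.095.
- Standard error = √(4/63 + 1/31) = 0.309.
- Noncentrality = 1.095/0.309 = 3.54. Welch df is about 92 and the two-sided critical value at 0.025 is 2.28.
- Power = 89.4% (normal approximation 90.3%). The d detectable with 90% power is 0.636.

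The claim therefore reproduces, with no margin. It does so only with an unequal-variance test and the df-weighted pooled SD. An unweighted pooled SD gives 82.5%, and a Student t test with the 2:1 SD ratio gives 76.6%.

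**2. Untreated share of the biopsy-to-biopsy interval.** Share = A/(A + 147 to 154 days), where A is the biopsy age at Day 0. The ages are assumed, because the documents give no distribution.

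| Assumed age at Day 0 | Untreated share |
|---|---|
| 3 months | 37–38% |
| 5 months | 50–51% |
| 6 months | 54–55% |
| 12 months | 70–71% |
| 24 months | 83% |

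**3. Effect on the mean difference.** Write the change as treatment effect + k × A + error, with the same k in both arms. The expected between-arm difference is the treatment effect + k × (mean A, PROSTVAC − mean A, placebo), and randomization makes the bracket zero in expectation. A simulation with ages assumed uniform over 0–36 months (Welch test, unweighted-pooled-SD scale) gave a difference of 0.99–1.00 against a true 0.996 at every drift size. Power fell from 83% without drift to 77%, 63% and 46% when drift added an SD of 0.5, 1.0 and 1.5 placebo SDs. The cost is variance, not dilution.

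**4. Sensitivity of the stated power.** Raw difference unchanged, SD of change in both arms multiplied by an assumed factor f. Effective d = 0.63/f; the N that holds power is 150 × f².

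| f | Effective d | Power | N to hold power |
|---|---|---|---|
| 1.0 | 0.63 | 89% | 150 |
| 1.1 | 0.57 | 82% | 182 |
| 1.2 | 0.53 | 75% | 216 |
| 1.3 | 0.48 | 67% | 254 |
| 1.5 | 0.42 | 53% | 338 |

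The documents give no absolute SD, no untreated drift in CD8 or CD4 and no biopsy ages, so they cannot say which row applies.

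**5. Grade endpoint, illustration only.** Section 2.1 cites 48% progression at 3 years in a control group, by pathologic or therapeutic criteria. That composite is not Gleason ≥4+3. Taking it as a constant hazard, h = −ln(0.52)/36 = 0.0182 per month. Assume a vaccine that halves the hazard for 5 months. Placebo risk is 1 − exp[−h(T + 5)] and vaccine risk 1 − exp[−h(T + 2.5)], with T the biopsy age in months.

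| T | Placebo risk | Vaccine risk | Ratio | Difference (points) |
|---|---|---|---|---|
| 0 | 8.7% | 4.4% | 0.51 | 4.2 |
| 3 | 13.5% | 9.5% | 0.70 | 4.0 |
| 12 | 26.6% | 23.2% | 0.87 | 3.4 |
| 24 | 41.0% | 38.2% | 0.93 | 2.7 |

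The ratio moves quickly toward 1; the absolute difference shrinks more slowly. With 90 and 45 men biopsied after 10% attrition, Fisher's exact test has about 15% power at T = 0 and 6% at T = 12. The comparison is therefore weak even with a fresh baseline.

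**The case against.** The strongest reply is that the trial is randomized and compares changes between arms, so untreated time is balanced in expectation and equal drift cancels. That stands for CD8, CD4, PD-L1, tumor extent and MRI lesion size, all of which are continuous. A reader might infer from the missing age limit that a real CD8 or CD4 effect is diluted; the algebra and the simulation show otherwise under equal drift.

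A reader might also infer that the changes span mostly untreated time. That is permitted but not shown: it requires a biopsy more than about 5 months old at Day 0, and no age distribution is given. Drift may be small, in which case so is the loss of power.

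The MRI window, with reports "performed from 3 years prior to and 6 months after the study intervention will be collected", invites a similar inference. It governs which reports are collected, if available, and does not select the baseline scan. The endpoint is an exploratory subgroup analysis, and an event-hazard model does not describe lesion size.

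The comparison with the PSA and DRE windows is also loose. Those windows govern eligibility, and a fresh PSA is drawn at the Baseline Visit, whereas a fresh baseline biopsy would be an additional invasive procedure.

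Finally, an interval covariate removes only average time-related drift. Man-to-man variation in drift remains. This is correct and limits what the fix can deliver.

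**Conclusion.** The point holds as one of precision. The baseline biopsy for both co-primary endpoints has no age limit, and the planned analysis ignores its age. The comparison stays unbiased and, with drift equal by arm, the mean difference is undiluted for continuous endpoints. The exposure is added variance against a stated 90% power that recomputes to 89.4%: about 82% or 75% if the SD of change is inflated by an assumed 10% or 20%. These factors are assumptions, and the true loss could be negligible.

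Dilution toward no effect applies only to the binary grade endpoint (8.2.5). That analysis is exploratory, and the ratios shown rest on a borrowed composite rate and an assumed halving of the hazard, so they indicate direction rather than size.

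The documents do not support going further. An eligibility limit on biopsy age would trade against accrual and against a post-intervention biopsy done as routine care. Excluding MRIs taken after definitive therapy would condition on a post-randomization event. Neither is recommended here. The proposed changes are a free improvement of modest and unquantified benefit.

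**What to change.** 1. In 13.4 and 13.5, record the date of the pre-intervention biopsy. The submitted pathology reports are de-identified (7.4), so capture the date, or the interval to Day 0, on the CRF. For CD8, CD4, PD-L1 and tumor extent, compare arms with a model that includes the biopsy-to-Day-0 interval, preferably together with the baseline value of the marker. Allow residual variances to differ by arm, since the stated power reproduces only under an unequal-variance test. Keep the 2.5% level for each co-primary endpoint.

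2. For 8.2.5 and 8.2.6, prespecify a sensitivity analysis in men whose baseline biopsy fell within 12 months of Day 0. The subgroup is defined by a pre-randomization variable. State that its power is low.

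Cost: one CRF field, a few sentences in the analysis plan and one degree of freedom per covariate. The trial already requests the biopsy records, and neither eligibility nor the visit schedule changes.

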4.2 Exclusion Criteria

- 4.2.1 Have had prior treatment for prostate cancer by surgery, irradiation, local ablative (i.e., cryosurgery or high-intensity focused ultrasound), or androgen-deprivation therapy.
- 4.2.2 Patients who have prostate cancer with distant metastases.
- 4.2.3 Have undergone treatment of hormone therapy, immunotherapy, chemotherapy and/or radiation for any malignancies within the past 2 years.
- 4.2.4 Uncontrolled intermittent illnesses or medical conditions which, in the opinion of the treating physician, would make this protocol unreasonably hazardous for the patient. Such illnesses/conditions may include, but are not limited to, ongoing or active infection, symptomatic congestive heart failure, unstable angina pectoris, symptomatic or unstable cardiac arrhythmia, or psychiatric illness/social situations that would limit compliance with study requirements.
- 4.2.5 Positive for HIV or active infections for hepatitis B, and /or hepatitis C, based on medical history.
- 4.2.6 Prior solid organ or bone marrow transplant.
- 4.2.7 Immunodeficiency or splenectomy.
- 4.2.8 Chronic immunosuppressive therapy within 30 days of screening.
- 4.2.9 Inflammatory eye disease requiring steroid treatment within 28 days of screening.
- 4.2.10 Chronic administration (defined as daily or every other day for continued use > 14 days) of systemic corticosteroids within 28 days of the first planned dose of PROSTVAC-V/F. Use of inhaled steroids, nasal sprays, and topical creams for small body areas is allowed.
- 4.2.11 History of or active autoimmune disease including but not limited to autoimmune neutropenia, thrombocytopenia, or hemolytic anemia, systemic lupus erythematosus, Sjogren's syndrome, scleroderma, myasthenia gravis, Goodpasture's syndrome. Persons with vitiligo are not excluded. Persons with well-controlled autoimmune endocrinopathies, e.g., diabetes mellitus, Graves' disease, Hashimoto's thyroiditis, Addison's disease are not excluded. Persons with well-controlled rheumatoid arthritis, psoriatic arthritis and polymyalgia rheumatica are not excluded.
- 4.2.12 Known allergy to eggs, egg products.
- 4.2.13 Prior or concurrent eczema or other eczematoid skin disorders or active skin condition (acute, chronic, or exfoliative) that disrupts the epidermis. Persons with psoriasis are not excluded except in cases of:
 - any active lesion
 - any active lesion in the previous 6 months that required treatment, either systemic or topical
 - any prior episode, at any time, extensive enough or severe enough as to require systemic treatment.
- 4.2.14 Previous adverse reactions to smallpox vaccination.
- 4.2.15 Unable to avoid close contact or household contact with the following high-risk individuals for three weeks after the Day 1 vaccination or until the vaccination site heals completely: (a) children \leq 3 years of age, (b) pregnant or nursing women, (c) individuals with prior or concurrent extensive eczema or other eczematoid skin disorders, (d) individuals with other acute, chronic, or

exfoliative skin condition, or (e) immunocompromised or immunosuppressed persons (by disease or therapy).

4.2.16 Participants may not be receiving any other investigational agents.

4.2.17 History of allergic reactions attributed to compounds of similar chemical or biologic composition of PROSTVAC®.

4.3 Inclusion of Women and Minorities

Men of all races and ethnic groups are eligible for this trial. Since women and children are not subject to prostate cancer, they will be excluded from this study.

4.4 Recruitment and Retention Plan

Study participants will be mainly recruited from patients seen at the institution urology clinics.

Additional recruitment methods include community physician referral, posting the study information on the institution websites, community outreach activities, and advertisement in print and web media.

The study team will provide a friendly and comfortable study setting for participants from initial contact through the completion of their study activities. Demands upon the subjects will be minimized to foster comfort while preserving the research goals. Wherever possible, flexibility will be built into the study schedule to promote compliance.

5. AGENT ADMINISTRATION

Intervention will be administered on an outpatient basis. Reported adverse events (AEs) and potential risks are described in Section 6.2.

5.1 Dose Regimen and Dose Groups

- The study agent is PROSTVAC®.
- Participants will be randomly assigned (2:1) to PROSTVAC® or placebo.
- One injection of PROSTVAC-V (or placebo) at baseline.
- Six injections of PROSTVAC-F (or placebo) over 140 days.

5.2 PROSTVAC® Administration

- Participants will receive subcutaneous injection of PROSTVAC® or placebo in the study clinic injected into the upper outer thigh or upper arm. It is recommended to alternate the injection sites.
- The treatment regimen will include a priming vaccination with subcutaneous injection of 2×10^8 pfu (in 0.5 mL) of PROSTVAC-V or placebo (empty vector) at baseline, followed by booster vaccinations with subcutaneous injection of 1×10^9 pfu (in 0.5 mL) of PROSTVAC-F or placebo (empty vector) on Day 14, 28, 56, 84, 112, and 140 following the priming injection.
- Participants should remain in the clinic for at least 30 minutes following administration of PROSTVAC-V/F or placebo for observation for signs of adverse reactions.

5.3 Run-in Procedures

Not applicable.

5.4 Contraindications

Participants will be reminded to avoid close contact or household contact with the following high-risk individuals for three weeks after the Day 1 vaccination or until the vaccination site heals completely: (a) children \leq 3 years of age, (b) pregnant or nursing women, (c) individuals with prior or concurrent extensive eczema or other eczematoid skin disorders, (d) individuals with other acute, chronic, or exfoliative skin condition, or (e) immunocompromised or immunosuppressed persons (by disease or therapy).

5.5 Concomitant Medications

All medications (prescription and over-the-counter), vitamin and mineral supplements, and/or herbs taken by the participant will be documented on the concomitant medication CRF and will include: 1) start and stop date, dose and route of administration, and indication. Medications taken for a procedure (e.g., biopsy) should also be included. Participants may receive other vaccines (e.g., flu, shingles, pneumonia) while on study. However, the non-study vaccines should not be given within a week of the PROSTVAC vaccine to avoid the confusion of potential AE symptoms of one vaccine versus the other. All non-study vaccines should be documented on the concomitant medication CRF.

